#### **14.2**

#### **Measures to Minimize Risks of Harm (Precautions, safeguards):**

For each research procedure or intervention, describe all measures to minimize and/or eliminate risk of harms to subjects and study personnel

As noted in the exclusionary criteria we will exclude participants who are using an FDA approved medication for AUD at the start of the study. There is no known risk to taking any of these medications concurrently with NAC, however, it is scientifically problematic to include participants taking these additional treatments. There are no other disqualifying concomitant medications.

Side effects will be managed as described in Section 16.1.

To minimize risks of side effects of virtual reality, participants will be screened prior to the virtual reality task to ensure they are safe to complete it. These procedures are outlined in the "NAC script" document. Participants who do not pass the screening will skip to the next procedure in the protocol.

To minimize risk of breach of confidentiality, records will be protected with data encryption technology, computer passwords, and locked cabinets. To protect against loss of PII we will use subject IDs on assessments.

#### **14.3**

#### **Confidentiality Protections (for research records, data and/or specimens):**

Describe in detail the plan to maintain confidentiality of the research data, specimens, and records throughout the study and at its conclusion (e.g., destruction, long term storage, or banking). Explain the plan for securing the data (e.g., use of passwords, encryption, secure servers, firewalls, and other appropriate methods). If data will be shared electronically with other team members/collaborators outside the institution, describe the method of transmission and safeguards to maintain confidentiality. Explain whether this study may collect information that State or Federal law requires to be reported to other officials or ethically requires action, e.g., child or spouse abuse

The information obtained will be stored electronically and in paper files in a secure location at USUHS Annex Building 53. Staff from the Institutional Review Board (IRB) at the Uniformed Services University and other government agencies as part of their duties, may look at these records to ensure privacy and security guidelines are followed. These duties include making sure that the research participants are protected.

Upon publication of research findings, deidentified data may be made open access consistent with an increasing number of journal policies. This enhances replicability, data aggregation, and potential scientific progress. For examples/further discussion, see:

<https://journals.plos.org/plosone/s/data-availability>

<https://www.frontiersin.org/articles/10.3389/fpubh.2017.00327/full>

The paper consent forms will be kept in a locked filing cabinet in [name] lab in a folder labeled with the participant ID for the duration of the study. These folders will only be accessible to approved study investigators and staff. At the end of the study, the consent forms will be

separated from the participant ID and maintained in a locked filing cabinet for three years, at which point they will be destroyed. The study email account will delete all outgoing messages to participants 3 years after completion of the study.

#### **14.4 Potential Benefits:**

Describe any real and potential benefits of the research to the subject and any potential benefits to a specific community or society

If the individuals in the research are considered experimental subjects (per 10 USC 980), and they cannot provide their own consent, the protocol must describe the intent to directly benefit all subjects

Individuals with AUD may see a reduction in alcohol use and co-occurring depression or anxiety by participating in the study, but there are no known benefits of NAC for AUD.

#### **14.5 Privacy for Subjects:**

Describe the measures to protect subject's privacy during recruitment, the consent process, and all research activities, etc.

Consenting and assessment will take place in a private room to ensure patient confidentiality and ensure patient has privacy to ask and answer questions.

#### **14.6 Incidental or Unexpected Findings:**

Describe the plan to address incidental findings and unexpected findings about individuals from screening to the end of the subject's participation in the research. In cases where the subject could possibly benefit medically or otherwise from the information, state whether or not the results of screening, research participation, research tests, etc., will be shared with subjects or their primary care provider. State whether the researcher is obligated or mandated to report results to appropriate military or civilian authorities and explain the potential impact on the subject

If the participant endorses a high level of suicidal ideation on the MADRS, the study investigator ([name]) will follow up as needed to recommend necessary care (as specified in the attached SOP).

Although unlikely given participants will be actively in care, or recently in care at ATS, they will be informed of any unexpected findings in the study physical and told to follow up with their primary care provider (e.g., previously undiagnosed hypertension).

There is a chance that participants could face legal consequences for public intoxication if they present intoxicated at the security gate before their study visit. Additionally, if their blood alcohol content is between .01 and .049, the research team will ask them to stay at the study location for their safety until it is below that threshold. If they refuse to stay, the research team will reschedule their appointment and the participant can leave. Furthermore, if the participant's BAC is  $\geq .05$ , they may need to be transported to the WRNMMC emergency room to assess potentially dangerous alcohol withdrawal. If they refuse to go to the emergency department, the research team may need to contact the local police to inform them of the situation.

### **15.0 Study Monitoring**

**15.1 Your study requires either Data and Safety Monitoring Plan (DSMP) or a Data and Safety Monitoring Board (DSMB).**

- DSMP
- DSMB
- Both
- Not Applicable

A DSMP should describe the plan to monitor the data to verify that the data are collected and analyzed as specified in the protocol. Include who will conduct the monitoring, what will be monitored, and the frequency of monitoring. It should also include the plan to ensure the safety of subjects

**Data Safety Monitoring Plan (DSMP)**

**Study Title:**

A pilot study of N-acetylcysteine for alcohol use disorder

**Type of Research Data or Events to be Monitored:**

We will monitor the collection, confidentiality, and security of all data collected in this study.

This monitoring plan will also maximize participant safety via the monitoring and reporting of adverse events and unanticipated problems as detailed in Section 16.0 Reportable Events and copy and pasted below for convenience.

**Methods and Frequency of Analysis:**

Data acquisition will be ensured during each session using checklist "flowsheets" (attached to the protocol). The PI will review the full collection of data at least monthly. All data will be stored in locked filing cabinets, secure USU computers, and deidentified data on secure google drive folders.

A study physician will conduct physical exams prior to enrollment and will monitor participants for side effects. Participants will be asked about adverse events weekly by the study physician. Participants may withdraw from the study at any time by contacting the research team, as stated in the consent form. The principal investigator may terminate any individuals' participation in the study at any time if he determines this to be in their best interest, if they are unable to comply with the procedures required, or if they no longer meet eligibility criteria.

**Person(s) Responsible for Data Monitoring:**

The data will be monitored by the principal investigator, [name], and the research team: [name], [name], [name], [name], and [name].

[name] will be responsible for submitting reports of unanticipated problems, serious adverse events, protocol deviations to the IRB and FDA as indicated.

**Incidental or Unexpected Findings will be handled as detailed in 14.6**

**Reportable Events and plan to respond is detailed in Section 16.0**

**16.0**

**Reportable Events**

**16.1 Reportable Events: Consult with the research office at your institution to ensure requirements are met. Describe plans for reporting unexpected adverse events and unanticipated problems. Address how unexpected adverse events will be identified, who will report, how often adverse events and unanticipated problems will be reviewed to determine if any changes to the protocol or consent form are needed and the scale that will be used to grade the severity of the adverse event.**

Consult with the research office at your institution to ensure requirements are met

- Describe plans for reporting expected adverse events. Identify what the expected adverse events will be for this study, describe the likelihood (frequency, severity, reversibility, short-term management and any long-term implications of each expected event)
- Describe plans for reporting unexpected adverse events and unanticipated problems. Address how unexpected adverse events will be identified, who will report, how often adverse events and unanticipated problems will be reviewed to determine if any changes to the research protocol or consent form are needed and the scale that will be used to grade the severity of the adverse event

### **Expected Adverse Events (EAEs)**

The primary EAEs for the study will be potential medication side effects.

Side effects are uncommon and relatively minor. The most frequently reported side effects are nausea, vomiting, and diarrhea. They often occur at identical rates to placebo. Rarely and primarily with intravenous administration, anaphylactic reactions may occur and can consist of rash, pruritus, angioedema, bronchospasm, tachycardia, and blood pressure dysregulation. Finally, given the limited reports on NAC in pregnant and lactating women, it should not be used in this population in the context of research and thus this is an exclusion criteria.

Sources: 1) FDA approved acetylcysteine labels (<https://dailymed.nlm.nih.gov/dailymed/index.cfm>)

To assess them, the study physician will use the Systematic Assessment for Treatment Emergent Events (SAFTEE) interview at each in-person appointment. This includes asking about common symptom indicators as well as an "other" option to record other side effects:

#### NAUSEA

*Minimal:* Single occurrence, lasting less than 2 hours; no change in eating habits

*Mild:* Multiple occurrences or duration longer than 2 hours; no change in eating habits

*Moderate:* Intake significantly less than minimum daily requirement, but able to eat

*Severe:* No significant nutritional intake

#### VOMITING

*Minimal:* Stomach contractions, retching, or heartburn without emesis

*Mild:* 1 episode in any 24-hour period

*Moderate:* 2-5 episodes in 24 hours or 1 episode per day on 5 or fewer days

*Severe:* 6-10 episodes in 24 hours or more than 1 episode on more than 5 days

#### DIARRHEA

*Minimal:* Loose but not watery stools, without cramping or incontinence

*Mild:* Diarrhea without cramping or incontinence

*Moderate:* Diarrhea with cramping, no incontinence

*Severe:* Diarrhea with incontinence and cramping

#### ABDOMINAL PAIN

*Minimal:* Single occurrence of abdominal pain that is not distressing and does not limit activities

*Mild:* Multiple occurrences of abdominal pain that is not distressing and does not limit activities

*Moderate:* Single or multiple occurrences of abdominal pain that causes distress but does not limit activities

*Severe:* Abdominal pain or cramping of sufficient severity to limit activities

#### CHANGE IN APPETITE

*Minimal:* Hunger increased or decreased without change in food intake or weight

*Mild:* Hunger increased or decreased, with change in food intake and pre-study weight stable or less than 5% reduction

*Moderate:* Hunger increased or decreased; change in food intake and 5%-10% weight loss or gain present without intention to diet or gain weight

*Severe:* Hunger increased or decreased; weight loss or gain of more than 10% of pre-study weight without intention to diet or gain weight

#### HEADACHE

*Minimal:* Single occurrence of headache that is not distressing and does not limit activities

*Mild:* Multiple occurrences of headache that is not distressing and does not limit activities

*Moderate:* Single or multiple occurrences of headache that causes distress but does not limit activities

*Severe:* Headache with pain of sufficient severity to limit activities

#### DIZZINESS

*Minimal:* Occasional transient subjective dizziness, lasting less than 1 minute per occurrence; no limitation of function and no objective findings

*Mild:* Subjective dizziness lasting greater than 1 minute; no objective findings and no impairment of function

*Moderate:* Dizziness with impairment of function or limitation of activities; nystagmus or increased body sway noted on exam

*Severe:* Dizziness with impairment of function, falling, or syncope

#### FATIGUE

*Minimal:* Subjective fatigue without increased need for rest; able to perform all activities of daily living (ADLs)

*Mild:* Subjective fatigue with increased need for rest; able to perform all ADLs

*Moderate:* Subjective fatigue with increased need for rest; able to perform ADLs only with effort  
*Severe:* Unable to perform ADLs; able to meet basic needs only with assistance

#### NERVOUSNESS/ANXIETY

*Minimal:* Occasional nervousness/anxiety that does not cause distress or limit activities

*Mild:* Occasional nervousness/anxiety that is distressing but tolerable and does not limit activities

*Moderate:* Occasional or persistent nervousness/anxiety that is distressing but tolerable and limits activities

*Severe:* One or more panic attacks or persistent nervousness/anxiety that is intolerable

#### INSOMNIA

*Minimal:* Sleep that is not restful, but without change in amount or pattern of sleep

*Mild:* More than between 1 and 3 occasions of unexplained difficulty falling asleep or of increased nocturnal awakenings, but without change in amount of sleep

*Moderate:* More than 3 occasions of unexplained difficulty falling asleep and nocturnal awakenings with significant reduction in sleep, but without daytime impairment of function  
*Severe:* More than 3 occasions of unexplained difficulty falling asleep and nocturnal awakenings with significant reduction in sleep, with daytime impairment of function

#### SOMNOLENCE

*Minimal:* Occasional subjective tiredness but without change in daily activities

*Mild:* Persistent subjective tiredness, but without change in daily activities

*Moderate:* Persistent subjective tiredness; requiring resting or napping less than 2 hours during the day

*Severe:* Persistent tiredness that significantly limits daily activities, requiring napping or resting more than 2 hours daily; falling asleep during work, school, or other activities

#### DEPRESSION

*Minimal:* Occasional depressed mood that does not cause distress or limit activities

*Mild:* Occasional depressed mood that is distressing but tolerable, and does not limit activities

*Moderate:* Occasional or persistent depressed mood that is distressing but tolerable, and is associated with a change in activities

*Severe:* Suicidal ideation or persistent depression that is intolerable and is associated with a change in activities

#### ITCHING

*Minimal:* Localized itching without need to scratch

*Mild:* Localized itching with scratching

*Moderate:* Generalized itching that is tolerable and does not interfere with sleep or activities

*Severe:* Generalized itching that is intolerable and interferes with sleep and/or activities

#### SKIN RASH

*Minimal:* Localized erythema or localized macular/ papular eruption, lasting less than 48 hours and without symptoms

*Mild:* Localized erythema or localized macular/ papular eruption, lasting greater than 48 hours and without symptoms

*Moderate:* Erythema or macular/papular eruption with pruritus or other associated symptoms involving more than one site on the body

*Severe:* Generalized (most of body affected) symptomatic macular, papular or urticarial or atypical eruption with or without mucous membrane involvement and with or without exfoliative dermatitis or ulcerating dermatitis

#### CHANGE IN LIBIDO

*Minimal:* Occasional increase or decrease in libido that does not engender distress or concern to the subject; no change in sexual activity or performance

*Mild:* More persistent libido increase or decrease that does not engender distress or concern to the subject; no change in sexual activity or performance

*Moderate:* More persistent libido increase or decrease that does engender distress or concern to the subject; changes in sexual activity or performance reported

*Severe:* Significant increase or total lack of interest in sex that is distressing or of concern to the subject; associated with changes in sexual activity or performance

#### **MISSED MENSES**

*Minimal:* Single occurrence of delayed menses (one cycle) that are otherwise regular

*Mild:* Single occurrence of absent menses (one cycle) that are otherwise regular

*Moderate:* Multiple occurrences of delayed or absent menses

*Severe:* Total amenorrhea

#### **Reporting EAEs**

All EAEs will be reported every 12 months to the IRB.

Moderate-Severe EAEs that are thought to be potentially attributable to the medication will be reported within 48 hours to the IRB. Additionally, the participant will be reminded of their choice to stop the medication and withdraw from the study at any time. The study physician will use medical judgement for requiring the participant to discontinue the medication and participation. Unblinding will occur in the event of a severe EAE that is thought to be related to medication or at the discretion of the study physician.

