### 9.3

#### Objectives/Specific Aims/Research Questions:

Describe the purpose and objective(s) of the study, specific aims, and/or research questions /hypotheses

The primary aim of the current study is to establish feasibility, dropout rate, and estimate the standard deviation of the outcome measures in order to estimate the required sample for a fully powered clinical trial and to refine the final measures for use in the fully powered clinical trial. The secondary aim is to explore preliminary efficacy signal of NAC. Specifically, we have primary, secondary, and tertiary hypotheses related to the putative effects of NAC: 1) NAC will reduce total drinking days and drinks per drinking day; 2) NAC will reduce alcohol cue-reactivity, alcohol demand on the alcohol purchase task (i.e., a measure assessing preferences for alcohol across a range of prices to determine the relative reinforcing value of alcohol), and trait-based craving; and 3) NAC will lead to improvements in response inhibition, working memory, processing speed, and executive functioning; and reductions in depression symptoms and anxiety symptoms. We will also explore change in total marijuana use days, total cigarette use days, and cigarettes per day in the subsets of individuals who use marijuana and cigarettes.

We anticipate this study will take 2 years to complete following approval (enrolling approximately 1 participant every other week).

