#### In-person visits (Wk 1, 3, and 5)

Participants will be temperature checked with a non-contact thermometer and screened for COVID symptoms. If their temperature is 100.4°F and above or they endorse any of the COVID symptoms, they will be rescheduled and told to get tested for COVID and see their primary care provider. Participants will be administered a breathalyzer by the research assistant (RA) to check BAC. If BAC is > 0, the RA will wait a few minutes and readminister. If BAC is 0, the RA will proceed with the study. If BAC is between .01 and .049, the RA will have the participant wait until it drops to 0. If the participant refuses to wait, the research team will reschedule their appointment and the participant can leave. If BAC is  $\geq .05$ , the participant will be transported to the WRNMMC emergency department to assess alcohol withdrawal. If the participant refuses to go to the emergency department, they will be informed that the research team will be forced to contact the NSA Bethesda police ([contact]) out of concern for their safety. A member of the study team will walk the participants unless by the judgement of the research assistant, the participant is unable to walk unassisted. In this case, we will contact 911 to dispatch a team to evaluate the participant and transport them as needed to the WRNMMC ED.

Female participants will be asked by the physician if they believe there's been a change to their pregnancy status since their last appointment. If they believe there has been a change, they will undergo a pregnancy screen using a pregnancy test kit, administered by the physician. If the screen is positive, they will be told they are no longer eligible to participate. Further, they will be instructed to contact their primary care provider to confirm the results and discuss the risks of alcohol use during pregnancy. The physician will then assess the participant for adverse events with the SAFTEE.

Next, the RA will conduct the pill counts, MADRS interview, then participants will complete the TLFB self-report form. Participants will then complete the computer questionnaires (APT, PACS, DDT, SIAS-6, SPS-6, and GAD-7) and behavioral tasks (Stop Signal, N-back, and Trail Making). These study sessions will take approximately 2 hrs to complete.

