**11.0 Statistical/Data Analysis Plan**

**11.1 Statistical Considerations:**

List the statistical methods to be used to address the primary and secondary objectives, specific aims, and/or research hypotheses. Explain how missing data and outliers will be handled in the analysis. The analysis plan should be consistent with the study objectives. Include any sub-

group analyses (e.g., gender or age group). Specify statistical methods and variables for each analysis. Describe how confounding variables will be controlled in the data analysis

Independent samples t-tests will be used to evaluate for differences in dropout rate and total adverse events between study groups.

For our exploratory aims, we will assess the treatment effects on variables of interest using linear mixed models. Given the exploratory nature of analysis, we will report both false discovery rate corrected and nominally significant findings. See 11.6 for more detail on planned analyses.

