**13.6 Withdrawal from Study Participation:**

Explain the process for withdrawal and specify whether or not the subjects will be given the opportunity to withdraw their data their data/specimens in the event they wish to withdraw from the study

Participants may withdraw at any time by calling or emailing the study team. The study phone number and email are provided on the informed consent form. Participants will not have the opportunity to withdraw their data at any point in the study. Study withdrawal will not impact participant medical care or status in the military.

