#### **Unexpected Adverse Events (UAEs) and Unanticipated Problems**

UAEs are AEs that are reported by the participants that are beyond the typical side effects of NAC. The study physician will provide guidance to the participant on whether they should discontinue the medication and study.

Unanticipated problems involving risks to participants will also be reported to the IRB. These events are a broader category of events than AE and can include breach of confidentiality, misplaced data, or other unexpected distress attributable to study participation.

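### Section 16.1 words a drug stop after an adverse event as also leaving the study, and no visible provision collects drinking outcomes off drug

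*Combined protocol and SAP*

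**What the plan says.** Section 16.1 joins stopping the drug with leaving the study in three places. Under Reporting EAEs, for moderate to severe expected events thought attributable to the drug, "the participant will be reminded of their choice to stop the medication and withdraw from the study at any time". The physician's power is then stated: "The study physician will use medical judgement for requiring the participant to discontinue the medication and participation". For unexpected events, the physician advises the participant "whether they should discontinue the medication and study".

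Section 15.1 lets the principal investigator end participation in the participant's best interest, or "if they are unable to comply with the procedures required, or if they no longer meet eligibility criteria". Section 13.6 describes only leaving the study: "Participants may withdraw at any time by calling or emailing the study team". It adds that data already collected cannot be withdrawn. The Clinical Follow-up Plan in 16.1 follows the adverse event itself and does not mention drinking outcomes.

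Dropout rate is part of the primary aim (9.3: "The primary aim of the current study is to establish feasibility, dropout rate"). Section 11.1 compares it between arms as a single quantity: "Independent samples t-tests will be used to evaluate for differences in dropout rate and total adverse events between study groups". The plan does not define dropout or separate it from stopping the drug.

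**The concern.** Stopping a drug and ending outcome follow-up are separate events. An analysis of all randomised participants by assigned arm needs the outcomes of people who stop treatment. If a drug stop also ends contact, their later drinking is not observed.

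The section 11.6 model has baseline outcome, arm, time point and their interaction as fixed effects, plus a participant effect. It uses whatever data exist without imputation. For someone removed after an adverse event, it therefore assumes that later drinking is missing at random given arm, baseline and earlier outcomes. In effect, that person's course is inferred from people in the same arm who stayed and who mostly still took the assigned capsules. Adverse events are not in the model. Sensitivity analyses are announced but not specified, so none is known to address this.

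The lesser issue is interpretation. With dropout undefined, one rate may mix people lost to contact with people who left because a drug stop was treated as an exit.

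**Working it through.** **1. The plan's own figure.** Section 11.5 asks for 40 participants plus 10 for dropout: 40 + 10 = 50, an implied 20% (10/50). Likewise 40/(1 − 0.20) = 50. The figure reproduces, and nothing here changes it.

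**2. Is off-drug follow-up provided anywhere visible?**
- 10.1 and the 10.2 schedule: visits and calls to week 7, with no early-termination or off-drug assessment.
- 11.6: the re-analysis above 80% adherence implies that poor adherers can stay, but it only narrows the sample.
- 10.1: starting an approved alcohol use disorder drug does not end participation.
- 18.2: the antidote entry suggests consulting the physician and considering stopping use, without mentioning exit.
- 13.6 and the Clinical Follow-up Plan: nothing on outcomes.

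So staying in off regimen is implied in places, but outcome collection after a stop for an adverse event is not stated.

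**3. Data at stake per exit.** Section 10.1 places TLFB at weeks 1, 3, 5 and 7 in person and at weeks 2, 4 and 6 by phone, giving 7 post-baseline contacts. An exit at week *w* loses 7 − *w* contacts if that contact's TLFB is done, and 8 − *w* if not. At in-person visits the physician's safety checks come before TLFB, so the second case is possible. Recovery calls are the remaining scheduled calls plus one at week 7.

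| Exit week | Lost, TLFB done | Lost, TLFB not done | Later calls needed |
|---|---|---|---|
| 1 | 6 | 7 | 4 (weeks 2, 4, 6, 7) |
| 2 | 5 | 6 | 3 (weeks 4, 6, 7) |
| 3 | 4 | 5 | 3 (weeks 4, 6, 7) |
| 4 | 3 | 4 | 2 (weeks 6, 7) |
| 5 | 2 | 3 | 2 (weeks 6, 7) |
| 6 | 1 | 2 | 1 (week 7) |

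**4. Effect on the dropout rate.** If such an exit is counted as dropout, it adds 1/50 = 2.0 percentage points overall, or 1/25 = 4.0 points in one arm. Taking 10 dropouts of 50 as an illustration, the exact (Clopper–Pearson) 95% interval is 10.0% to 33.7%. A few such exits lie well inside that uncertainty.

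**5. Effect on the standard deviations.** The 95% limits for a pooled SD are √(df/χ²) times the estimate, with df = evaluable − 2. With 40 evaluable (df 38) they are 0.82 to 1.29 times the SD. With 35 (df 33) they are 0.81 to 1.32 times. Even five exits contributing nothing would hardly matter.

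**The case against.** The strongest reply is that the coupling is read from conjunctions in safety-reporting text. The reminder to participants may simply list two rights, the advice on unexpected events is guidance, and the physician's power is discretionary. Sections 10.1, 11.6 and 18.2 show that people off regimen can remain, and visits are not made conditional on taking capsules. The detailed study script and the consent form were not available and may say more. All of this stands, so the claim is that data could be lost, not that they must be. It does not remove the point: the physician's sentence names drug and participation together, and nothing visible says what happens to outcome collection.

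Four stronger readings are tempting but unsupported.
- *Every adverse-event stop forces an exit.* The text leaves it to judgement.
- *Each exit uses up one of the 10 dropout places.* Data already collected are kept (13.6), and the mixed model uses them (11.6). A late exit may have supplied most of its drinking data.
- *The main trial would be missized.* If that trial keeps the same exit rules, it will have the same exits, and counting them is right. The documents do not fix its rules.
- *Pregnancy exits are an equal problem.* Section 10.1 says of an on-study test: "If the screen is positive, they will be told they are no longer eligible to participate". Women trying to conceive within 4 months are excluded, treatment lasts 7 weeks, and ending participation is a protective choice.

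**Conclusion.** The point holds as a low-cost improvement. Following the wording of 16.1 when a drug stop is required or advised could end drinking-outcome collection for that person, at a loss of between 1 and 7 of 7 contacts depending on timing. The all-participant analysis would then rest on missing-at-random for people who left for a reason the model does not contain.

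The number affected is not given and is probably small, since 16.1 describes side effects as uncommon. Neither the direction nor the size of any bias can be derived from the documents. The efficacy analyses are exploratory, and the sample size and SD precision are essentially unaffected. The conclusion assumes that the script and consent form contain no off-drug follow-up rule; if they do, only the wording of 16.1 and the reporting of exits need attention.

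**What to change.** In 13.6, 15.1 and 16.1, define *discontinued study drug* and *withdrew from study* as separate events. Leave unchanged who stops drug and when. Ask participants who stop for an adverse event to complete TLFB at that contact and then on the remaining scheduled calls plus one at week 7, unless they withdraw consent. Include those data in the all-participant analysis, and flag any collected after unblinding, which 16.1 prescribes for severe drug-related events. Define dropout, and report drug discontinuation and study withdrawal separately by arm with reasons, so that the main trial can use whichever rate matches its own exit rules. Phone TLFB after a positive pregnancy test can be left optional, subject to the IRB.

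The cost is protocol and consent wording, 4, 3 or 2 calls after a stop at week 1, 3 or 5 (TLFB itself takes 5 minutes according to 10.2), and some open-label self-report. A leaner variant would reuse the window of up to 30 days allowed at the first meeting. One week 7 call would then cover a stop at week 3 or later (7 × 4 = 28 days), and two would cover a stop at week 1 or 2 (42 or 35 days), at the price of longer recall.
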